Study population: Patients hospitalized for cellulitis, > 18 years of age.

Power calculation (non-inferiority design): a total sample size of 316 randomized patients gives 80% power to reject the null hypothesis of non-inferiority assuming a 15% failure rate, considering a difference of 10% as equivalence limit, with a 0.05 significance level.

Intervention: 6 days of flucloxacillin followed by another 6 days of flucloxacillin or placebo.

Main study parameters/endpoints: The primary endpoint is resolution of cellulitis at 14 days, defined as disappearance of warmth and tenderness at the site of infection, with substantial improvement in erythema and edema, and without recurrence by day 28, defined as the need of additional antibiotic therapy for cellulitis.

Secondary study endpoints include a test of cure with a different set of criteria for cure by day 14 and relapse by day 28, recurrence of cellulitis by day 90, speed of recovery as determined by improvement in cellulitis severity score and self assessment of subjective pain and swelling on VAS scales (0-10), Health-related Quality of Life (Dutch SF-36 questionnaire), and health care resource utilisation as determined by total antibiotic use and effect on direct and indirect health-care associated costs (economic evaluation and budget impact analysis).

Statistical analysis: Analysis will be based on intention-to-treat basis. Groups will be compared for the primary endpoint with Chi-squared test and Cochran-Mantel-Haenszel test for adjustment for the baseline covariates to evaluate the non-inferiority hypothesis. Secondary outcome parameters will be analyzed using Chi-squared test, two group t-test or Mann-Whitney test when appropriate.

Nature and extent of the burden and risks associated with participation: All study participants will have to complete a maximum of five sets of questionnaires (some by phone) and a maximum of five venous punctures. Potential risks include inferiority of 6 days of antibiotics compared to 12 days of treatment, i.e. a slower recovery of patients in the intervention group. Given the results of earlier trials on shortening of antibiotic therapy in pneumonia and urinary tract infections, we do not expect this to be the case. In our view the

small risk that 6 days will be inferior compared to 12 days offsets the profits which a shortening of antibiotic therapy for cellulitis potentially yields.

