3. STUDY DESIGN

3.1 Design

The DANCE study is a prospective, randomized, observer, physician and patient blinded, placebo-controlled, multicentre non-inferiority trial with two parallel groups. Patients hospitalized with cellulitis and responding to initial therapy, defined as absence of fever (temp > 38.0°C) and improvement in cellulitis severity score (self-reported or investigator-assessed) by day 5, will be randomized with a 1:1 allocation into one of two groups, who will receive different treatments after the 6th day:

- Regular treatment group: after the initial 6 days of flucloxacillin, another 6 days of oral flucloxacillin.
- Intervention group: after the initial 6 days of flucloxacillin, 6 days of oral placebo.

Study protocol is based on the SPIRIT 2013 guidance for clinical trial protocol development¹⁸.

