4.4 Sample size calculation

The sample size calculation of is based on three large randomised clinical trials which were published in high impact journals in 2014. From the DISCOVER, ESTABLISH and SOLO trials, information was gathered on cellulitis clinical cure rates as assessed by investigators after therapy:

DISCOVER²¹ (dalbavancin vs vancomycin-linezolid): (information from supplementary data)

- Clinical status evaluation at the end of therapy (day 14) of cellulitis patients:
 - o Cured: 297/324 and 276/301

ESTABLISH²⁷ (tedizolid vs linezolid): (information received from authors via e-mail)

- Investigator assessed response at post-therapy evaluation (7-14 days after end of therapy) of cellulitis patients:
 - o Cured: 265/301 and 263/307

SOLO²⁸ (oritavancin vs vancomycin): (information received from authors via e-mail)

- Investigator assessed clinical cure rates at the post-therapy evaluation (7-10 days after end of therapy) of cellulitis patients:
 - o Cured: 294/387 and 315/400

Total cure rates:

- $$(297+276+265+263+294+315) / (324+301+301+307+387+400) = 1710 / 2020 = 84,65\% \text{ cure rate}$$

A two-group large-sample normal approximation test of proportions with a one-sided 0.050 significance level will have 80% power to reject the null-hypothesis, assuming a success rate

of 85% and considering a difference of 10% between the two groups as equivalence limit, if the sample size of each group is 158. This gives a total sample size of 316 patients.

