7.5 Replacement of individual subjects after withdrawal

Not applicable, an intention-to-treat analysis will be performed.

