9. STATISTICAL ANALYSIS

9.1 General considerations

For the modified intention to treat analysis, all randomized patients who received at least one dose of study medication will be included. Missing data will be handled with multiple imputation, due to its nature of giving standard errors and P values that incorporate missing-data uncertainty²².

For the per protocol analyses, only randomized patients whose compliance was clear, and who received at least four days of trial medication (in clinical successes), or one day of trial medication (in clinical failures) will be included.

For the per protocol analysis of our primary outcome, patients are considered clinically cured if there is resolution of cellulitis at 14 days defined as disappearance of warmth and tenderness at the site of infection, with substantial improvement in erythema and edema, and without recurrence by day 28, defined as the need of additional antibiotic therapy for cellulitis. Clinical failure is defined as the persistence or progression of signs and symptoms of the acute process after randomization, or the inability to complete the study owing to adverse events. The response is deemed indeterminate when the patient (i) received less than 80% of the study drug for reasons other than clinical failure, (ii) acquired a concomitant infection outside of the skin requiring antibiotic treatment, (iii) was lost to follow-up, or (iv) died unrelated to the primary diagnosis.

For the per protocol analysis of our first secondary outcome (paragraph 7.1.2), patients are considered clinically cured if there is resolution of cellulitis at 14 days, defined as the absence of fever and an improvement of the combined symptom score of warmth, tenderness, erythema and edema by 2 or more points since patient inclusion (or it has reached 0), and without recurrence by day 28, defined as a stable or further improved combined symptom score, absence of fever and no need of additional antibiotic therapy for cellulitis. The response is deemed indeterminate when the patient (i) received less than 80% of the study drug for reasons other than unblinding / requiring new antibiotics for cellulitis / being unable to continue due to adverse effects, (ii) acquired a concomitant infection outside of the skin requiring antibiotic treatment, (iii) was lost to follow-up, or (iv) died unrelated to the primary diagnosis. Those whose outcomes are not cured or indeterminate are considered clinical failures.

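### The per-protocol rules turn an established failure on the first secondary outcome into indeterminate after a later loss, infection or unrelated death, and leave the order unstated for the primary outcome

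*Combined protocol and SAP*

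**What the plan says.** Section 9.1 gives two sets of per-protocol outcome rules.

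For the first secondary outcome there is a definition of cure and a list of indeterminate criteria. Everything left over is failure: "Those whose outcomes are not cured or indeterminate are considered clinical failures".

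For the primary outcome, failure has its own definition (signs and symptoms that persist or progress after randomisation, or inability to complete the study because of adverse events). It stands beside a similar indeterminate list.

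In both lists item (i) concerns patients who took less than 80% of study drug, and it has exemptions. The primary version exempts clinical failure. The secondary version exempts unblinding, new antibiotics for cellulitis and adverse effects. The remaining items have none. They apply to any patient who "acquired a concomitant infection outside of the skin requiring antibiotic treatment, (iii) was lost to follow-up, or (iv) died unrelated to the primary diagnosis".

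The per-protocol set is described only through successes (at least four days of trial drug) and failures (at least one day). Section 9.1 does not say in so many words that indeterminates are left out. The main analysis is modified intention-to-treat with multiple imputation. Table 3 lists per protocol among the sensitivity analyses, under a non-inferiority hypothesis.

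**The concern.** A cure on either composite needs information up to day 28-29, but a failure can be settled sooner. Suppose cellulitis progresses and antibiotics are restarted on day 11. Nothing that happens afterwards can turn that patient into a cure. Yet if the patient is then lost, is treated for pneumonia or dies of something else, the rule for the first secondary outcome files the case as indeterminate. For the primary outcome two analysts could classify the same patient differently, and both would be following the text.

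This looks like an omission. The exemptions in item (i) and the one-day drug minimum for failures both show an intent to keep early failures, and items (ii) to (iv) undo it. The situation is also foreseeable. Section 8.2.2 expects a significant part of patients to be readmitted for relapse, and section 7.6 describes usual care after withdrawal from treatment without specifying outcome visits. In a non-inferiority trial the per-protocol result is read as a check on the main analysis, so its categories should be fixed before the data are seen.

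**Working it through.** **Base case.** Section 4.4 gives a "one-sided 0.050 significance level will have 80% power to reject the null-hypothesis", "considering a difference of 10% between the two groups as equivalence limit", and 85% success (the Summary has it as "assuming a 15% failure rate"). Allocation is 1:1 (3.1). The unpooled normal approximation gives

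n per arm = (1.645 + 0.842)² × 2 × 0.85 × 0.15 / 0.10² = 157.7, rounded up to 158.

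This reproduces the plan: "This gives a total sample size of 316 patients". The size is not in dispute. It only supplies the arms for the illustration.

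**Which rule wins.**

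- First secondary outcome: failure means neither cured nor indeterminate. A patient who meets (ii), (iii) or (iv) is indeterminate, so cannot be a failure. The rule is stated, and it misclassifies a known failure.
- Primary outcome: failure and indeterminate are defined separately and can both be met. No order is given.

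**Illustration.** Inputs that are not in the documents are assumptions: true failure of 25% (short course) and 15% (standard course), so that the difference sits at the margin, and the shares of failures (qF) and cures (qC) removed as indeterminate. In each arm, with true failure rate F,

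observed failure = F(1 − qF) / [F(1 − qF) + (1 − F)(1 − qC)].

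For example, with qF = 10% and qC = 0: 0.225/0.975 = 23.1% and 0.135/0.985 = 13.7%.

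| Removed as indeterminate | Short | Standard | Difference (points) |
|---|---|---|---|
| Nobody | 25.0% | 15.0% | 10.0 |
| 5% of failures, both arms | 24.1% | 14.4% | 9.7 |
| 10% of failures, both arms | 23.1% | 13.7% | 9.4 |
| 20% of failures, both arms | 21.1% | 12.4% | 8.7 |
| Same share of failures and cures | 25.0% | 15.0% | 10.0 |
| 10% of cures only, both arms | 27.0% | 16.4% | 10.6 |
| Failures: 5% short, 20% standard | 24.1% | 12.4% | 11.7 |
| Failures: 20% short, 5% standard | 21.1% | 14.4% | 6.7 |

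In patients, 10% of failures is 158 × 0.25 × 0.10 = 4.0 (short) and 158 × 0.15 × 0.10 = 2.4 (standard). If both true rates are 15%, equal removal leaves the difference at 0.

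**Chance of passing a 10-point test.** If the rule of section 9.3 were applied to the per-protocol set, this would be Φ((0.10 − d)/SE − 1.645). At 10% of failures removed, d = 0.0937 and SE = √(0.231 × 0.769/154 + 0.137 × 0.863/156) = 0.0437, which gives Φ(−1.50) = 6.7%. With nobody removed it is 5.0%; at 5% and 20% removed it is 5.8% and 9.1%.

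**Planned per-protocol measure.** Table 3 specifies relative risk here. With 10% of failures removed, the relative risk of failure goes from 25/15 = 1.67 to 1.68, so it does not shrink. The relative risk of cure, the scale on which Table 3 states the outcome, goes from 75/85 = 0.882 to 76.9/86.3 = 0.891, slightly towards 1.

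**The case against.** The strongest reply is that the gap is narrow and its effect unknown. Much of that stands.

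- A reader might infer that indeterminate outranks failure throughout the per-protocol rules. The text supports that only for the first secondary outcome. For the primary outcome it is silent on order, which is an ambiguity and not a rule.
- A reader might infer that the rule necessarily pulls the arms together. It does not. Items (ii) to (iv) remove would-be cures too, and equal removal changes nothing. Item (i), which exempts failures, and the four-day against one-day drug minimum tend to remove cures, which works the other way. Removal mainly of standard-course failures widens the difference.
- A reader might infer a raised risk of a false non-inferiority claim for the trial. The 10-point decision belongs to the primary analysis in 9.3. Table 3 gives per protocol a chi-squared test and relative risk, with no 10-point rule.
- Few patients may be affected. Section 3.3 allows a telephone visit at day 28-29 in exceptional cases, 5.5 offers home visits, 11.1 has later antibiotic use checked with the pharmacy when in doubt, and 8.5 expects low mortality. No document supports 10% or 20% removal.
- The quoted sentence could be parsed so that indeterminates count as failures. That would leave the category with no purpose, so it is the less natural reading.

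None of this answers the classification point. Under the natural reading, a patient with a known failure on the first secondary outcome is set aside because of a later, unrelated event.

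**Conclusion.** The defect is real and limited. For the first secondary outcome, the rule as written reclassifies established failures as indeterminate. For the primary outcome, it leaves their class open. Exclusion of indeterminates is inferred, because the per-protocol set is described only by successes and failures.

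The bias runs towards non-inferiority if the short course is worse and failures are removed more often than cures, and not mainly from the standard arm. Under the assumed 25% and 15%, that costs 0.3 to 1.3 points when 5% to 20% of failures and no cures are removed. The documents give no rates of loss, other infection or unrelated death, so neither sign nor size can be settled from them. The sample size and the modified intention-to-treat result do not change. A clarification is still worth making, because it is cheap and removes a choice that could otherwise be made after the data are seen.

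**What to change.** In 9.1, for both per-protocol analyses, keep every existing definition of cure, failure and indeterminate, including item (i) and failure through inability to complete the study because of adverse events. Then add four statements:

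1. A patient who meets a failure criterion before any event under (ii) to (iv) remains a clinical failure. Because the first secondary outcome has no failure definition of its own, say that this means any component of cure already observed not to be met.
2. Items (ii) to (iv) apply only when the event comes before failure and before the day 28-29 outcome is known. A cure already established at day 28-29 therefore stays a cure.
3. Indeterminate patients are excluded from the per-protocol set.
4. Indeterminates are reported by arm and by reason.

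The cost is a change of wording, with no effect on sample size or conduct. Per-protocol cure rates fall slightly. Would-be cures lost before day 28 are still removed while known failures are kept, so the difference may widen a little (about 10.6 points if 10% of cures are removed, under the assumptions above). That is the cautious direction for non-inferiority and should be stated alongside the result.

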9.2 Baseline characteristics

Statistical analysis will be based on the intention-to-treat principle. Baseline assessments and outcome parameters will be summarized using simple descriptive statistics.

Continuous variables will be summarized with standard descriptive statistics (e.g. mean, median, interquartile ranges, etc). Categorical variables will be summarized with frequencies and percentages. Ninety-five percent confidence intervals will be provided for descriptive statistics, as warranted.

Characteristic	6-day group	12-day group
Age (yr)		
Male sex (%)		
Ethnicity/race (white/black/asian/other)		
BMI (kg/m ²)		
No. of days of symptoms before presentation (days)		
Antibiotic treatment preceding presentation (%)		
Risk factors:		
- diabetes mellitus (%)		
- peripheral arterial disease (%)		
- lymphoedema (%)		
- non-diabetic ulcer (%)		
- venous insufficiency (%)		
- eczema / dermatitis (%)		
- trauma (%)		
- immunosuppression (%)		
- tattoos (%)		
- burns (%)		
- tinea pedis (%)		
- none (%)		
Cellulitis lesion surface area at presentation (cm ²)		
Axillary or inguinal lymphadenopathy (%)		
Resident at health care centre (%)		
Previous episode(s) of cellulitis (%)		
Smoker (%)		
Temperature at presentation (°C)		
Leukocyte count (x10 ⁹ /l)		
C-reactive protein (mg/l)		
Initial cellulitis severity score (score)		
Total % of positive cultures (%)		
- Streptococcus pyogenes (%)		
- Staphylococcus aureus (%)		
- MRSA (%)		
- Other Gram+ (%)		
- Gram- (%)		
Duration of hospital stay (days)		

Table 2. Baseline characteristics to be collected

9.3 Primary study parameter(s)

For the primary outcome, the proportion of successful treatments will be calculated for the two groups, and the absolute risk difference (with one sided 95% confidence limit) will be estimated to evaluate the non-inferiority hypothesis. In a secondary analysis, the difference in proportion in the two groups will be adjusted for relevant baseline covariates, using a logistic regression analysis. The difference in proportion of successful treatments will be estimated at mean values for the covariates.

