7.2 Randomisation, blinding and treatment allocation

Patients who respond to initial therapy will be randomized in a 1:1 ratio at day 5 by the commonly used online ALEA® randomisation software to one of two arms (starting at day 6):

(A) Standard course: after 6 days of flucloxacillin, another 6 days of oral flucloxacillin.

(B) Short course: after 6 days of flucloxacillin, 6 days of oral placebo.

The independent central randomisation service will create a computer generated random schedule in permuted blocks, stratified for diabetes mellitus (yes or no) and study site. The code will only be broken in case the DSMB advises to do so.

Hospital pharmacies are closed during the weekends, but there is a possibility that patients need to be evaluated for their day 5-6 timepoint somewhere during the period between Friday 16:00, and Monday 9:00, while they also need to receive their first dose of study medication in that period. For those patients, normal randomisation would be unfit because the study medication can't be delivered in time. For this minor group of patients, a different method of randomisation is used:

- Before Friday afternoon (ideally on the day 2-3 visit), the researchers will evaluate if the patient is likely to be randomised during the weekend period. If that is the case, the default checks in the eCRF are bypassed, and the patient is preliminarily randomised, thus assigning a randomisation number, and allowing the pharmacy to prepare the appropriate medication.
- Medication for these patients will be prepared by the AMC pharmacy, even if patients are admitted to other study sites. The researchers will collect the medication and store it in their workspace.
- Upon evaluation of the patient during the day 5-6 timepoint, the researchers will judge if the patient is able to be randomised according to the randomisation criteria.
 - o If the patient **can** be randomised, the medication will be given as if the patient was randomised as normal. Data entry will be done on the same day, and the built-in eCRF checks will automatically be performed during the night, confirming the appropriate randomisation.

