9.4 Secondary study parameter(s)

Differences in secondary outcome parameters will be reported as relative risk or mean difference (with 95% confidence interval), and p-values for statistical significance estimated with the Chi-square test, t-test or Mann-Whitney test, where appropriate. A Kaplan-Meier analysis will be performed to compare the time to relapse (defined as requiring additional antibiotics for cellulitis) between the two groups.

Variable/outcome	Hypothesis	Outcome measure	Methods of analysis
1. Primary			
Resolution without relapse	Intervention not inferior to control	Percent cured on day 14 without relapse by day 28 [binary]	Absolute risk difference
2. Secondary			
Resolution without relapse (per definition of protocol version 9.4, see paragraph 7.1.2, including both sensitivity analysis and per protocol analysis)	Intervention not inferior to control	Percent cured on day 14 without relapse by day 28 [binary]	Absolute risk difference (Per protocol analysis: χ^2 → Relative Risk)
Relapse by day 90	No difference	Percent with relapse [binary]	χ^2 → Relative Risk
Time to relapse	No difference	Relapse after cure [time to event]	Kaplan-Meier survival analysis
Objective speed of recovery	No difference	Cellulitis severity score [continuous]	Student's T-test or Mann-Whitney U test
Subjective speed of recovery	No difference	Visual analogue scales of pain and swelling [continuous]	Student's T-test or Mann-Whitney U test
Quality of life	No difference	SF-36 questionnaire score at day 0 and 90 compared to population, day 14 and 28 compared to day 5-6 [continuous]	Student's T-test or Mann-Whitney U test
Antibiotic usage	No difference	Total costs of antibiotic use [continuous]	Student's T-test or Mann-Whitney U test
Health care utilization	No difference	Total treatment associated costs, Health Care Utilization Questionnaire [continuous]	Student's T-test or Mann-Whitney U test
3. Subgroup analyses			
Cellulitis severity score on a continuous scale	Severity score affects rate of cure		Regression analysis, with interaction term for severity score
Diabetes mellitus vs no diabetes mellitus	Diabetes affects rate of cure		Regression analysis, with interaction term for (no) diabetes
4. Sensitivity analyses	Intervention not inferior to	All outcomes	

	control		
Per protocol analysis			Chi ² → Relative Risk
Primary outcome adjusted for baseline covariates			Cochran-Mantel-Haenszel → Relative Risk

Table 3. Analysis methods per outcome measures or variables

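### Randomisation is stratified by diabetes and site but the primary risk difference uses neither; if either predicts cure, the non-inferiority limit is slightly wider than it need be

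*Combined protocol and SAP*

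**What the plan says.** Section 7.2 uses a "random schedule in permuted blocks, stratified for diabetes mellitus (yes or no) and study site".

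Section 9.3 takes the proportion of successes in each group and says "the absolute risk difference (with one sided 95% confidence limit) will be estimated to evaluate the non-inferiority hypothesis". The primary row of Table 3 (section 9.4) gives only an absolute risk difference. No stratification factor appears in either place.

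Adjustment is mentioned in three other places, and they do not agree:

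- Section 9.3: "In a secondary analysis, the difference in proportion in the two groups will be adjusted for relevant baseline covariates, using a logistic regression analysis". The covariates are not listed, and the difference is evaluated at their mean values.
- Table 3, under sensitivity analyses: "Cochran-Mantel-Haenszel → Relative Risk" for the primary outcome adjusted for baseline covariates.
- Summary, statistical analysis: a chi-squared test together with a "Cochran-Mantel-Haenszel test for adjustment for the baseline covariates to evaluate the non-inferiority hypothesis".

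None of the three names diabetes or site. Section 9.1 expects diabetes to affect outcome, but it enters the analysis only as a subgroup interaction. The sample size in section 4.4 rests on "A two-group large-sample normal approximation test of proportions", which is an unstratified test.

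**The concern.** Blocking within strata balances diabetes and site across the arms, so differences between strata contribute little to the sampling error of the risk difference. The crude standard error still counts them. When the strata are prognostic, the crude limit is therefore wider than the sampling error of the estimate warrants, and some power is given away.

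The planned adjusted analyses do not make good the omission. A relative risk cannot be read directly against an absolute margin: 10 points below 85% is a ratio of 75/85 = 0.88, but that ratio changes with the control rate. A difference at mean covariate values is not the marginal risk difference to which the 10-point margin applies. Because the Summary ties a covariate-adjusted test to the non-inferiority hypothesis while 9.3 does not, a reader also cannot be sure which analysis is decisive.

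**Working it through.** **Inputs from the documents.** 85% success in both arms, 10-point margin, one-sided alpha 0.05, 80% power, 158 per group (4.4). 1:1 allocation, strata diabetes by site (7.2). Three academic centres plus 8 affiliated hospitals (4.1), so up to 11 sites, 22 strata and 316/22 = 14.4 patients per stratum on average.

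**Assumptions, because the documents give no figures.** Diabetes prevalence 15 to 35%, cure-rate gap by diabetes 0 to 20 points, between-site SD of the cure rate 0 to 8 points, and blocks of 4 in the simulations.

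**1. The plan's own figure.** n = (1.645 + 0.842)² × 2 × 0.85 × 0.15 / 0.10² = 157.7, so 158 per group, as stated. The crude standard error is sqrt(2 × 0.85 × 0.15 / 158) = 0.0402. The limit lies 1.645 × 0.0402 = 6.61 points below the estimate, and power is 80.1%.

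**2. Effect of the strata.** With diabetes prevalence p, gap g and site SD s, the share of outcome variance explained by the strata is R = [p(1 - p)g² + s²] / (0.85 × 0.15). The stratified standard error is the crude one times sqrt(1 - R). Power with the stratified limit is Φ(0.10/SE_strat - 1.645). Power with the crude limit under the same stratified randomisation is Φ((0.10 - 1.645 × SE_crude)/SE_strat).

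Example with p = 25%, g = 15 points, s = 5 points: R = (0.1875 × 0.0225 + 0.0025)/0.1275 = 0.053, and the distance is 6.61 × sqrt(0.947) = 6.43 points.

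| Prevalence, gap, site SD | R | Distance to limit, stratified (crude 6.61) | Power, crude limit | Power, stratified limit |
|---|---|---|---|---|
| 25%, 0, 0 | 0 | 6.61 | 80.1% | 80.1% |
| 25%, 10, 3 | 0.022 | 6.54 | 80.3% | 80.8% |
| 25%, 15, 5 | 0.053 | 6.43 | 80.7% | 81.9% |
| 25%, 20, 5 | 0.078 | 6.34 | 81.0% | 82.9% |
| 35%, 20, 8 (extreme) | 0.122 | 6.19 | 81.6% | 84.4% |

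The excess width is 0.07, 0.18 and 0.27 points in the three middle rows and 0.42 in the extreme one.

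**3. Simulation, 6,000 trials per scenario** (11 sites, 25% diabetes), crude limit against the Mantel-Haenszel risk difference:

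- No effect: distance 6.57 against 6.59 points, power 80.4% against 80.3%.
- Gap 15, SD 5: 6.58 against 6.43, power 81.7% against 82.8%.
- Gap 20, SD 5: 6.58 against 6.33, power 80.4% against 82.0%.
- True 10-point deficit, all scenarios: non-inferiority was declared in 5.0 to 5.5% of trials with the crude limit and 5.1 to 5.7% with the stratified one. The Monte Carlo error is sqrt(0.05 × 0.95/6000) = 0.3 points.

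**4. Simulation on the logit scale, 8,000 trials per scenario.**

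- Site SD 0.5 and diabetes odds ratio 2: standard error 0.0398 to 0.0391, which is 1.645 × 0.0007 = 0.12 points on the limit; power 80.5% to 81.2%.
- Site SD 0.7 and odds ratio 3: 0.0398 to 0.0381, or 0.28 points; power 80.4% to 82.8%.
- No stratum effect: the stratified standard error is 0.3% larger. A separate run gave 0.04022 against 0.04004, or 0.5%.

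**The case against.** The best defence is that design and analysis already agree. The sample size was set on the same unstratified test, "with a one-sided 0.050 significance level will have 80% power to reject the null-hypothesis", and 158 per group reproduces without any help from the strata. The documents do not size the effect of diabetes and nowhere say that site predicts cure, so the gain could be nil. With up to 22 strata, and about 316 × 0.25/11 = 7 patients in each diabetic stratum at 25% prevalence, stratifying can cost a trace of precision. All of this stands. It makes the change an improvement rather than a repair, but it does not explain why two factors important enough to stratify on are absent from the decisive limit.

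Two stronger readings are tempting. A reader might infer that the trial falls short of its planned power; it does not, because the crude analysis keeps at least 80.1%. A reader might also infer that the crude test runs clearly below its nominal 5%. The large-sample formula leans that way (4.8%, 4.6% and 4.3% in the three middle rows of the table), but the simulated crude rates ranged from 4.2% to 5.5% depending on assumed site sizes and effects. With no prevalence, effect size, block size or site size in the documents, no particular error rate can be claimed.

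**Conclusion.** The point holds in a limited form. The primary estimate and its limit leave out both stratification factors, and no planned adjusted analysis supplies a stratified difference on the absolute scale. If diabetes or site predicts cure, the cost is about 0.1 to 0.3 points of limit width in moderate to strong scenarios (about 0.4 at the extreme), or roughly 1 to 2 points of power. If neither does, there is no cost. All sizes rest on the assumed prevalence, effects, site number and block size. Leaving out the strata errs on the cautious side, so a non-inferiority claim from the crude limit would not be unsafe on this account. Separately, and without any assumption, the Summary, 9.3 and Table 3 describe the analysis of non-inferiority differently and need to be reconciled.

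**What to change.** - In 9.3 and Table 3, make the primary estimate a risk difference on the absolute scale that uses diabetes and site, with its one-sided 95% limit against -10 points. Either a Mantel-Haenszel-weighted difference over the strata, with its stratified variance, or a marginal difference standardised over a model with arm, diabetes and site would serve.
- State the rule for pooling small sites in advance, based on numbers randomised and blind to arm and outcome.
- Say how the estimate and its variance are combined across the multiple imputations planned in 9.1, and include arm, diabetes and site in the imputation model.
- Keep the crude risk difference as a sensitivity analysis.
- Make the Summary, 9.3 and Table 3 name this one primary analysis, and list the covariates of any further adjusted analysis.

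The cost is plan wording and the choice of a pooling rule; both factors are already recorded. The standard error rises by about 0.3 to 0.5% if neither factor is prognostic. Since the simulated error of the stratified limit sat at or slightly above 5%, its variance formula should be checked by simulation at the actual site sizes before unblinding.
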